6.7 RT Treatment

- 6.7.1 Radiotherapy will begin on Day 1 of therapy.
- 6.7.2 SBRT fractions to each individual site may occur at most 3 times per week, but never on consecutive days.
- 6.7.3 SBRT fractions to the different sites of involvement may occur on the same day or on different days per patient and physician preference.
- 6.7.4 All radiotherapy must be completed by Day 28 of radiation, unless an adverse event occurs to delay treatment
- 6.7.5 Prior to each fraction of SBRT, patients will be brought to the treatment room and placed in the treatment position using custom immobilization. Cone-beam CT prior to administration of fraction to confirm appropriate patient set-up is preferred if available and indicated, but alternatively patients may have pre-treatment KV portal imaging.

6.8 Radiotherapy Adverse Events

Please refer to Section 8 for details regarding radiotherapy adverse events and adverse event reporting.

7. RISKS AND BENEFITS

7.1 RADIOTHERAPY ADVERSE EVENTS

Adverse event (AE) monitoring and reporting will be performed. Please refer to Section 5.2 for definition of Dose Limiting Toxicity.

Radiotherapy reactions will be defined as acute or late as defined below:

Acute Reactions: Acute side effects are considered as occurring ≤ 90 days from the start of radiation therapy. They will be documented using the NCI Common Terminology Criteria for Adverse Events (CTCAE) version 4.0 (ctep.cancer.gov/reporting/ctc.html).

Late Reactions: Late side effects are considered as occurring > 90 days from the start of radiation therapy through a 12 month total evaluation period. They will also be documented using the NCI Common Terminology Criteria for Adverse Events (CTCAE) version 4.0 (ctep.cancer.gov/reporting/ctc.html).

Alopecia, skin hyperpigmentation, and erythema are likely in all treatment fields. It is likely that all patients treated on study will develop some level of fatigue. Rarely, some patients may have a vasovagal response before, during, or after SBRT fractions.

Other side effects of treatment will vary depending on the location of disease and volume of normal tissues in the radiation therapy portals. All attempts should be made to minimize side effects by limiting the normal tissue in the radiation therapy portals and adhering to the normal tissue dose constraints of this study.

7.1.1 Additional Adverse Events Associated with stereotactic radiation to the brain.

Acute Reactions: Expected acute reactions include transient small amounts of bleeding and swelling (including in sites of frame placement for radiosurgery), transient head/neck pain/discomfort, transient nausea and vomiting, and headache. Rare toxicities include infection of stereotactic frame pin sites, intracranial or extracranial hemorrhage, vasovagal response to frame placement.

Late Reactions: Edema of treated lesion is expected on imaging, but this is often asymptomatic. Unlikely toxicities include persistent nausea, vomiting or headache. Rare toxicities include radionecrosis, lethargy, somnolence, damage to the eye with the possibility of blindness, cataracts, severe neuropsychological dysfunction, hearing loss, pituitary dysfunction, cranial neuropathy.

7.1.2 Additional Adverse Events Associated with Head and Neck radiotherapy.

Acute Reactions: Depending on the structure irradiated in the region, possible but expected toxicities include pharyngitis, esophagitis, laryngitis, mucositis, xerostomia, xerophthalmia, voice hoarseness, otic changes, dysgeusia, dysphagia, odynophagia. Other possible but less likely acute reactions include sinusitis, pruritis of external auditory canal, pharyngotympanic dysfunction, mucosal hemorrhage, and weight loss.

Late Reactions: Unlikely toxicities include xerostomia, dental caries, dysgeusia, tracheoesophageal fistula, vascular rupture, hypothyroidism. Cataracts are possible but uncommon. Other possible but rare late effects include damage to the eye with the possibility of blindness, accelerated atherosclerosis, severe neuropsychological dysfunction, damage to spinal cord, brachial plexopathy, symptomatic esophageal stricture.

7.1.3 Additional Adverse Events Associated with Lung/Mediastinal Radiation

Acute Reactions: Cough and esophagitis (if the esophagus is included in the radiation therapy portal) are likely. Severe esophagitis (requiring IV hydration, therapy interruption, or severe cough), shortness of breath, and hemoptysis are possible but less likely.

Late Reactions: Asymptomatic fibrotic changes in the lung seen on chest imaging are likely. Severe pneumonitis or fibrosis of lung resulting in severe respiratory compromise, symptomatic esophageal stricture, radiation pericarditis, and myocardial injury, spinal cord injury, and brachioplexopathy are possible but unlikely side effects of radiation.

7.1.4 Additional Adverse Events Associated with Abdominal/Pelvic Radiation

Acute Reactions: Anorexia, diarrhea, nausea, and vomiting are likely but dependent on the volume of stomach and bowel in the treatment fields. Urinary urgency and dysuria are likely if the bladder is in the radiation therapy fields. Severe nausea, vomiting, and/or diarrhea that requires therapy interruption or IV fluid replacement, abnormal liver function or renal function tests, and low

blood counts are less likely but possible. Pain with defecation and mild to severe rectal bleeding are possible.

Late Reactions: hepatitis, nephritis, bowel obstruction or perforation, radiation cystitis, or proctitis are possible but unlikely. Erectile dysfunction is also unlikely. Damage to spinal cord is possible but unlikely.

7.1.5 Additional Adverse Events Associated with Radiation to the Soft Tissues or Bones in the Extremities

Acute Reactions: Minor skin reactions are likely; moist desquamation is possible but unlikely.

Late Reactions: Swelling of the treated region and poor wound healing are possible but unlikely. Pathologic fracture of the bone, severe debilitating swelling, weakness, and radiation-induced neoplasm are possible but unlikely. Fibrosis of extremity and joints with resulting pain and/or decreased extremity function is possible but unlikely.

7.1.6 Additional Adverse Events Associated with Radiation to the Spine

The possible acute and late toxicities of radiation to the spine will include those that affect radiation to the region of the body in which the spine is being treated (i.e. head and neck, chest, abdomen, pelvis). Additionally, rarely, patients could develop damage to the spinal cord or cauda equina resulting in severe neurologic dysfunction/paralysis.

7.1.7 Treatment of Adverse Events:

All attempts should be made to limit the symptoms and the overall impact of acute and late effects of radiation. Side effects of treatment may be treated per standard of care supportive agents.

8. Adverse Event Reporting

University of Chicago Reporting Guidelines

8.1 If the adverse event requires reporting, the Research Nurse or MD reports the adverse reaction to the Cancer Clinical Trials Office (CCTO) at [contact] by the end of the business day when he/she becomes aware of the event. Events occurring after business hours will be reported to the CCTO by 12 pm (noon) the next business day.

8.2 The following information is required when calling in the event:

- Caller's Name and Telephone Number
- Patient Initials
- Patient Medical Record Number
- IRB Protocol Number
- PI of Study
- Attending Physician
- Date of Event
- Description of Event (including grade of the event and attribution of the event and if the event required hospitalization)

8.3 E-mail is sent to the research nurse, attending physician and PI of the study informing them that adverse reaction notification has been received.

8.4 The University of Chicago's IRB Serious Adverse Event Form must be sent to the CCTO within **5 calendar days of event occurrence**. The UC IRB Serious Adverse Event form is available on-line at: <http://ors.bsd.uchicago.edu/HS/newirbforms>. This form must be typed. Once the forms are completed, the original is forwarded to the study PI to review and sign. The signed report is delivered to the QA Coordinator. A weekly report of delinquent or pending documents will be forwarded to the applicable person who reported the event. All delinquent reporting (greater than

10 days from event occurrence) must include documentation of reason for delinquency and may require implementation of an action plan.

8.5 Once the appropriate AE documents have been received, the CCTO forwards these to the IRB. A copy will be forwarded to the appropriate Research Nurse.

9. Data Safety and Monitoring

Data Safety and Monitoring will occur at the weekly University of Chicago GU oncology phase I/II conference meetings, which are lead by senior level medical oncologists. At each meeting, all active studies will be reviewed for safety and progress toward completion. Toxicities and adverse events will be reviewed at each meeting and a Data Safety and Monitoring form will be completed for each protocol and signed by either the Principal Investigator, the Chairman of the Department or by his designate if the Chairman is not available.

10. STUDY CALENDAR

Baseline CBC, serum chemistry, and pregnancy test (if indicated) are to be conducted within 30 days prior to study registration. Scans and x-rays must be done ≤6 weeks prior to study registration.

	Pre-Study	Wk 1	Wk 2	Wk 3-4	1 Mo Post-RT [^]	2 Mo Post-RT [^]	3 mo Post-RT [^]	6 mo Post-RT [^]	9 mo Post-RT [^]	1 yr Post-RT [^]
Radiotherapy		R	R	(R)						
Informed Consent	X									
Medical History	X	X	X	X	X	X	X	X	X	X
Concurrent meds	X	x	X	X	X	X	X	X	X	X
Adverse Events evaluation		X	X	X	X	X	X	X	X	X
Clinic Visit	X	X	X	X	X	X	X	X	X	X
Pain Assessment	X	X	X	X	X	X	X	X	X	X
CBC/platelets	X	X*			X*		X*			
Serum chemistry ^a	X	X*	X*	X*	X*		X*	X*	X*	X*
Plasma [#]	X						X	X		X
Radiographic imaging ^b	X						X	X	X	X
B-HCG ^c	X									

[^]: Date of post-treatment visit will correspond to the start date (first day) of SBRT

R: Radiotherapy: 10 Gy x 5 fractions, or maximum safe dose to all extracranial sites, and size based SRS

a: Albumin, alkaline phosphatase, total bilirubin, bicarbonate, calcium, chloride, creatinine, glucose, LDH, phosphorus, potassium, total protein, SGOT [AST], SGPT [ALT], sodium.

b: CT of the head, chest, abdomen, and pelvis, and any other pertinent imaging based on clinical situation are required within 28 days of each visit.

c: Serum pregnancy test (women of childbearing potential)

*: CBC and serum chemistry may be obtained per physician discretion following initial assessment. However, it is required to check AST and ALT if SBRT is delivered to liver, at each week of RT, at 1 month post-RT, and at each q3 month follow-up interval (3, 6, 9, 12 months post-RT).

#: For patients who provide consent

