3. PATIENT SELECTION

3.1 Eligibility Criteria

- 3.1.1 Patients must have histologically or cytologically confirmed metastatic or recurrent RCC (any histologic subtype).
- 3.1.2 Patients must have between 1 to 5 new or recurrent lesions suspicious for metastatic RCC on diagnostic imaging.
 - 3.1.2.1 Each extracranial lesion must be ≤ 6 cm and amenable to SBRT or surgical excision.
 - 3.1.2.2 Patients must have 3 or fewer brain metastases, of size ≤ 4 cm.
 - 3.1.2.2.1 Brain metastases must be treated prior to enrollment in the study. The modality of treatment of brain metastases can include surgical resection, whole brain radiotherapy, stereotactic radiosurgery, or any combination of the above.
 - 3.1.2.3 Patients who have an intact unresected primary tumor should be considered for radical nephrectomy and primary resection prior to enrollment in the study. If the patient is not eligible for surgical resection, the primary tumor must be amenable to SBRT or RFA. Generally, this will be defined as a primary tumor <10 cm in size or a primary lesion which can be treated to a dose of ≥ 8 Gy x 5 without excessive perceived risk of toxicity.
- 3.1.3 Patients must have had at least a CT of the chest, abdomen, and pelvis within 4 weeks of registration in the trial. CT or MRI of the brain is only required in the presence of neurologic symptoms.
- 3.1.4 Patients must have had no radiotherapy, immunotherapy, chemotherapy or therapy with targeted agents within the last 1 month.
- 3.1.5 Patients may not have had prior bevacizumab, based on case reports of tracheo-esophageal fistula in patients treated with bevacizumab and radiotherapy [58, 59].
- 3.1.6 Age ≥ 18 years. Because of the risk of adverse events in patients <18 years of age, children are excluded from this study, but will be eligible for future pediatric SBRT trials.

- 3.1.7 ECOG performance status ≤ 2 (see Appendix A).
- 3.1.8 Life expectancy of ≥ 3 months.
- 3.1.9 Patients must have normal organ and marrow function within 30 days of registration, as defined below:
- absolute neutrophil count $\geq 500/\text{mcL}$
 - hemoglobin $\geq 8.0 \text{ g/dL}$
 - platelets $\geq 50,000/\text{mcL}$
 - total bilirubin within normal institutional limits
 - AST(SGOT)/ALT(SGPT) $\leq 3X$ institutional upper limit of normal if liver metastases are present
- 3.1.10 Women of childbearing potential must have a negative pregnancy test within 14 days of registration.

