12. STATISTICAL CONSIDERATIONS

12.1 Study Design/Endpoints

This is a pilot study of the use of 5-fraction SBRT for oligometastatic RCC. Patients enrolled in the study will be treated with SBRT to all sites of disease. Enrollment will proceed according to a sequential toxicity monitoring schema [69] to test the null hypothesis of a $\pi_0=5\%$ grade 4 toxicity rate against an upper acceptable boundary of a $\pi_1=20\%$ grade 4 toxicity rate. Trial enrollment will be halted if there are two grade 4 events within the first 2 patients, if there are three events within the first 14 patients, or if there are four events within the first 25 patients. The treatment will be considered successful if there are less than four events in 25 patients, i.e., $<16\%$ observed toxicities. This design has approximately 80% power (78.8%) to declare the treatment too toxic if the true grade 4 toxicity rate is $\pi_1=20\%$.

Patients will be followed for a total of one year after completion of the trial per protocol. Patients may be treated with off-protocol systemic therapy no earlier than 2 weeks after completion of RT. The primary endpoint is the rate of grade 4 RT-related toxicity with this treatment approach. Secondary endpoints include determining the toxicity profile of 5-fraction SBRT, determining the feasibility of 5-fraction SBRT based on normal tissue dosimetric constraints based on the organ site of involvement, describing the LeC, PFS, and patterns of failure of this approach, as well as to explore the feasibility of accrual and the adequacy of the eligibility criteria of this approach.

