12.4 Analysis of the Primary Endpoint

The primary endpoint is the rate of grade ≥ 4 RT-related toxicity with this treatment approach. RT-related toxicity will be recorded as specified in the study calendar (section 10). All toxicity will be determined to be RT-related or non-RT-related by the study committee.

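### Toxicity is recorded by a calendar with no pre-treatment adverse event grade and, except for AST/ALT after liver SBRT, no required post-baseline blood test, which mainly weakens the toxicity profile

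*Combined protocol and SAP*

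**What the plan says.** Section 12.4 makes the calendar the instrument for the primary endpoint: "RT-related toxicity will be recorded as specified in the study calendar (section 10").

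In the section 10 calendar:

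- The row "Adverse Events evaluation" has no mark at Pre-Study and is marked at every column from week 1 to one year.
- Medical history, concurrent medication, clinic visit, pain assessment, CBC and serum chemistry are all marked at Pre-Study.
- Every later CBC and chemistry mark carries an asterisk, whose footnote reads "CBC and serum chemistry may be obtained per physician discretion following initial assessment". The next sentence of that footnote makes AST and ALT compulsory after liver SBRT: in each week of RT and at 1, 3, 6, 9 and 12 months.

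Section 11.1.1 counts every patient as evaluable for toxicity from the first treatment, whatever tests are done. The synopsis (definition of the primary endpoint) and section 5.2 leave attribution to a study group or committee, which looks at the region treated, the timing and the nature of the event. Section 7.1.4 lists "abnormal liver function or renal function tests" and low blood counts among the possible acute reactions to abdominal or pelvic treatment, and nephritis among the late ones.

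**The concern.** A toxicity profile needs two things from the visit schedule: a starting grade, so that new findings can be told from old, and the same tests in everyone, so that a missing abnormality means something. The calendar secures neither for laboratory terms, and it does not secure the first for symptoms.

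Patients may enter with abnormal values. Section 3.1.9 admits neutrophils from 500/mcL, hemoglobin from 8.0 g/dL and platelets from 50,000/mcL. It allows AST/ALT up to three times the "institutional upper limit of normal if liver metastases are present", and it lists no creatinine limit. Patients with metastatic disease may also bring pain and other symptoms. If none of this is graded, a descriptive table of toxicity mixes prior disease with the effect of SBRT.

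After baseline, an untested patient remains in the all-treated denominator and is in effect counted as free of laboratory toxicity. Whether an event is seen then depends on who orders a test.

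**Working it through.** **1. Setting the sections side by side**

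| Item | Before treatment | After treatment starts |
|---|---|---|
| Adverse event evaluation | not marked | every visit |
| CBC | required | week 1, months 1 and 3, all discretionary; no mark elsewhere |
| Chemistry, including creatinine | required | weeks 1, 2 and 3-4, months 1, 3, 6, 9 and 12, all discretionary |
| AST/ALT, liver treated | required | required |

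Table 1 sets kidney dose limits to protect renal function, and section 6.5.1 allows SBRT to the primary tumor. The plan therefore requires laboratory follow-up of an irradiated liver but not of an irradiated kidney. Neither section 5.2 nor section 12 names baseline grade, worsening from baseline, or the handling of a test not done.

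**2. Reproducing the plan's power**

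Inputs from section 12.1: "null hypothesis of a $\pi_0=5\%$ grade 4 toxicity rate"; "upper acceptable boundary of a $\pi_1=20\%$ grade 4 toxicity rate"; and the rule beginning "Trial enrollment will be halted if there are two grade 4 events within the first 2 patients", then 3 in 14 and 4 in 25. Event counts cannot fall, so the trial runs to the end without halting only if there are at most 1 event in patients 1-2, at most 2 by patient 14 and at most 3 by patient 25.

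Let s be the number of events by patient 14, excluding the path with two in the first two. At a rate of 0.20, the first two patients give 0 or 1 event with probability 0.64 or 0.32. The next twelve give 0, 1 or 2 with probability 0.06872, 0.20616 or 0.28347.

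- P(s=0) = 0.64 × 0.06872 = 0.04398
- P(s=1) = 0.64 × 0.20616 + 0.32 × 0.06872 = 0.15393
- P(s=2) = 0.64 × 0.28347 + 0.32 × 0.20616 = 0.24739

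The last eleven patients give at most 3, 2 or 1 events with probability 0.83886, 0.61740 or 0.32212.

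P(no halt) = 0.04398 × 0.83886 + 0.15393 × 0.61740 + 0.24739 × 0.32212 = 0.2116, so P(halt) = 0.7884. This matches the stated 78.8%. The same calculation at 0.05 gives a false-halt probability of 5.0%. The design arithmetic is sound.

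**3. What misclassification would do, if there were any**

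The documents give no misclassification rate, so both shares below are assumptions and both ranges start at zero. If a share m of true events is missed at a true rate of 20%, the observed rate is 0.20 × (1 − m). If a share a of patients has a prior abnormality scored as an event at a true rate of 5%, the observed rate is 1 − 0.95 × (1 − a).

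| Missed share m | Observed rate | P(halt) |
|---|---|---|
| 0% | 20% | 78.8% |
| 5% | 19% | 75.2% |
| 10% | 18% | 71.1% |
| 20% | 16% | 61.7% |

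| Falsely scored share a | Observed rate | P(false halt) |
|---|---|---|
| 0% | 5.0% | 5.0% |
| 1% | 5.95% | 8.0% |
| 2% | 6.9% | 11.6% |

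These rows show only how the rule behaves at other event rates. They do not show that any row other than the first applies.

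**The case against.** The strongest reply is that the primary endpoint is largely protected. An event must be grade 4 or higher and be judged RT-related on region, timing and nature. An abnormality already present before the first fraction should fail on timing, and the baseline history, pain assessment and laboratory values needed to see this are collected. To be missed, an event would have to be laboratory-only, outside the AST/ALT requirement, clinically silent at every scheduled visit, and never tested. Discretionary testing with one organ-specific requirement can also be a deliberate choice in a 25-patient pilot of local treatment.

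Most of this stands for the primary endpoint, and it rules out three stronger readings that a reader might infer:

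- *That all post-baseline testing is discretionary.* The same footnote requires AST/ALT after liver SBRT.
- *That pre-existing abnormalities will be counted as primary events.* Attribution makes this unlikely. How near the entry limits lie to grade 4 depends on CTCAE thresholds that the documents do not give.
- *That the halting rule is biased toward success by a known amount.* Missed tests push toward success and wrongly scored prior findings push toward halting. The net direction is not established, and no missed share can be derived from the documents.

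The reply does not reach objective 1.2.1. The two-part test of grade and attribution protects the grade 4 count. It does not supply baseline grades or uniform testing for a description of toxicity at all grades.

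**Conclusion.** The point holds as a weakness of ascertainment, chiefly for the secondary toxicity profile. Followed as written, the plan yields ungraded baseline findings and laboratory data driven by clinical suspicion, with no rule for either. For the primary endpoint, the missed-test effect is limited to clinically silent, laboratory-only, RT-related events of grade 4 or higher. Its size is unknown and may be near zero. With a cut-off of 4 in 25, one misclassified patient could change the conclusion, but nothing in the documents says how likely that is. Any power illustration should be left out or shown as a range that includes no loss.

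The conclusion assumes that the calendar and its footnote are applied literally and that no instruction outside these documents requires baseline grading or laboratory tests. It is a cheap improvement that should be made, not a flaw in the design.

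**What to change.** (a) Mark "Adverse Events evaluation" at Pre-Study. Record baseline CTCAE v4.0 grades from the history, pain assessment and laboratory values already collected, and tabulate worsening from baseline. The committee then has the starting grade before it.

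(b) For endpoint ascertainment, obtain CBC and chemistry, including creatinine, in all patients at the visits already marked with the asterisk. This leaves blood counts unscheduled at weeks 2 and 3-4 and at months 2, 6, 9 and 12, and the report should say so.

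(c) For each laboratory term, report the number tested and the number not assessed alongside the all-treated denominator. Do not use a tested-only rate as the sole estimate while testing is discretionary. Testing prompted by suspicion would inflate it, just as counting the untested as event-free deflates the other.

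Cost: an edit to the calendar and its footnote, an edit to the case report form, and a few routine blood tests. Section 14.1 already assumes routine phlebotomy at baseline and at 3, 6 and 12 months. No dose, treatment or halting rule changes. For patients already treated, laboratory grades at baseline can be derived from stored values, but tests never drawn cannot be recovered.
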